3.1. Background

Presence and severity of non-motor symptoms modulates the rate of Parkinson's Disease (PD) progression with a high impact on patients' quality of life [1-3]. One major clinical milestone in the course of the disease is the conversion to Parkinson's disease dementia (PDD), dramatically increasing the risk for nursing home placement and mortality [4]. One of the greatest risk factors for PDD is the development of mild cognitive impairment in PD (PD-MCI) [5]. However, only a subgroup (26% to 39.1%) of patients with PD-MCI have been reported to convert to dementia, while others present with a stable cognitive status or revert to normal cognitive function [6-8]. For an early and effective treatment, the identification of a high-risk group for PDD among those with PD-MCI is essential.

The core feature that differentiates PDD from PD-MCI is the loss of the ability to perform activities that are necessary for independent living [9, 10], emphasizing the importance of valid and reliable activities of daily living (ADL) assessments in PD [11]. To confirm the diagnosis of PDD, ADL disabilities should be primarily caused by cognitive, not motor, dysfunction [10, 12]. As PD is primarily a movement disorder, the distinction between motor and non-motor contributions to ADL in PD is an obvious challenge [13].

ADL can be divided into basic (e.g. self-maintenance skills) and instrumental functions (e.g. complex skills). Of these, instrumental ADL function is impaired in the earlier stages whereas basic ADL can be preserved for a long time [14]. In Alzheimer's disease (AD), the combination of slight ADL impairment and mild cognitive impairment increases the risk for dementia, as opposed to the presence of only one of these characteristics [15, 16]. In PD, there is also evidence to assume that mild ADL impairments in PD-MCI characterize those patients at high risk for PDD, as mild signs of ADL impairment are observed in a subgroup of PD-MCI patients as a potential prodromal sign for PDD [14, 17-20]. So far, only a few studies have focused on the interaction between cognitive performance and ADL function in PD. First reports indicate that the cognitive profile of those PD-MCI patients with and without mild signs of ADL impairment does not differ [18, 21]. This implicates that (i.) neuropsychological tests lack predictive value for PDD [22, 23], (ii.) the ADL instruments used might not be suitable to detect cognitive-driven ADL impairment as they cover the characteristic motor signs of PD, or (iii.) sample sizes of previous studies were too small to reveal a between-group effect. Therefore, an economic and valid ADL measure for cognitive decline is needed to evaluate the prognostic value of mild ADL impairment for PDD conversion. We propose the follow-up of an already existing large, non-demented baseline PD cohort to longitudinally investigate the association between ADL function and cognitive performance along with blood and cerebrospinal Fluid (CSF) biomarker profiles.

3.2. Preliminary data

Methods. In a cohort of 216 non-demented PD patients (41.2%, with PD-MCI), assessed within the frame of the ongoing "Amyloid-Beta in Cerebrospinal Fluid as a Risk Factor for Cognitive Dysfunction in Parkinson's Disease" (ABC-PD) study, we developed a novel quotient score from the Pfeffer Functional Activities Questionnaire (FAQ) [24]. The FAQ is a 10 item instrumental ADL assessment scored on a 4-point Likert scale ranging from normal (score=0) to dependent (score=3) ADL function (max. points 30) [25].

The novel FAQ quotient was developed by differentiating cognitive and motor aspects of the individual items. Ten linear regressions were conducted defining each FAQ item as the dependent variable, and the Unified Parkinson's Disease Rating Scale-Part III (UPDRS-III), motor assessment) as well as the Montreal Cognitive Assessment (MoCA) total score as independent variables, with age, sex, and disease duration entered as covariates.

Results Part 1: Construction of FAQ-Quotient. As a result, the items 1-(accounting for finances), 2-(tax/business records) and 9-(remembering important events) showed associations with the MoCA score, whereas the items 3-(shopping alone), 4-(skills & hobbies), 5-(using appliances), 6-(meal preparation), 10-(traveling out of house) were found to be significantly associated only with the UPDRS-III score. Item 7-(current events) and 8-(information intake) were associated with both motor and cognitive function and were therefore included into both scores as a constant. Based on the regression analyses, the set of items for cognitive function was defined as, $S_{cog} = \{1,2,7,8,9\}$ while the set of items reflecting motor function was defined as $S_{mot} = \{3,4,5,6,7,8,10\}$. If S_i denotes the score obtained in item i for a patient and $S_{i,max}$ denotes the maximum score possible for item i , then the following subscores were defined as:

$$FAQ_C = \sum_{i \in S_{cog}} \frac{S_i}{S_{i,max}} \quad FAQ_M = \sum_{i \in S_{mot}} \frac{S_i}{S_{i,max}} \quad FAQ_Q = \frac{FAQ_C + 1}{FAQ_M + 1}$$

FAQ_Q: The quotient was formed by dividing the cognitive aspect (FAQ_C) by the motoric aspect (FAQ_M); a value >1 (FAQ_{Q>1}) indicates more cognitive- compared to motor-related ADL impairment.

Results Part 2: Validation of FAQ-Quotient. Out of the 89 PD-MCI patients, 32.6% presented with FAQ_Q values >1 , while 67.4% had an FAQ_Q ≤ 1 . The frequency of males was comparable between both PD-MCI subgroups (FAQ_{Q>1} 65.5%, FAQ_{Q≤1} 63.3%; $p=0.99$). Logistic regression analyses showed that patients defined as PD-MCI FAQ_{Q>1} were more impaired in tests assessing attention/working memory ($p=0.033$) and language performance ($p = 0.019$) than the PD-MCI FAQ_{Q≤1} group, while motor symptom severity revealed no significant difference between groups ($p=0.095$). Therefore, subgrouping PD-MCI patients according to the cognitive and motor performance in the FAQ is suitable for differentiating between different levels of severity for cognitive impairment in PD.

4. Objectives of the study

The FAQ is an economic and easy to apply ADL scale. Items of the FAQ have been previously published [25, 26]; details of the construction of our FAQ parameters are currently under review for publication and will also be available without additional costs.

The aim of our project is to evaluate whether the combination of PD-MCI along with cognitive-driven ADL impairment predicts the future development of PDD and might be able to differentiate between those PD-MCI patients with a high risk for the development of PDD from those with stable PD-MCI. The identification of a high-risk group for PDD among those with PD-MCI is essential for upcoming clinical trials targeting cognitive impairment in its earliest stages.

4.1. Hypothesis and research questions

Based on previous reports and preliminary results, we hypothesize that PD-MCI patients with a more pronounced cognitive-driven ADL impairment (FAQ_{Q>1}) are at higher risk for conversion to PDD than PD-MCI patients with ADL impairment primarily related to motor function (FAQ_{Q≤1}).

1. Stratification of subgroups according to their baseline cognitive status (PD-MCI vs. normal cognition, PD-CN) and ADL function (cognitive-driven (FAQ_{Q>1}) vs. motor-driven (FAQ_{Q≤1})).
2. Defining progression of ADL impairment over time.
Aim 2.1: Evaluation of stability and/or progression of ADL status between baseline and follow-up (FAQ_{Q>1} vs. FAQ_{Q≤1}).
3. Evaluation of the interaction between cognition and ADL function over time.
Aim 3.1: Evaluation of conversion rates to PD-MCI and PDD according to baseline ADL status (FAQ_{Q>1} vs. FAQ_{Q≤1}).
Aim 3.2: Prediction of PD-MCI (among PD-CN) and PDD according to baseline ADL, cognitive, genetic, and biomarker profiles in blood and CSF.
Aim 3.3: Progression of decline in cognition and ADL function in relation to Amyloid and Tau burden.

5. Study duration

Total duration of the study is 2 ½ years.

6. Study population

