6.3. Recruitment

Participants of the already recruited ABC-PD cross-sectional cohort (ethic protocol 686/2013B01) will be asked to participate in the follow-up assessment. Patients who did not agree to participate in a longitudinal study or who have asked not to be contacted after the first cross-sectional assessment will not be contacted again. A drop-out rate of 20% is expected for follow-up retention. Therefore, investigation of 209 patients will be conducted between August 2018 and April 2020. During the executive project phase, three patients will be assessed weekly (~12 per month). Patients will be contacted either via phone or in written form. Reason for drop-outs will be registered for data analysis.

7. Statistics and Sample size estimation

The relative risk as well as the positive and negative Likelihood Ratios according to baseline group status for conversion to PD-MCI or PDD will be calculated.

1. Between-group differences will be conducted using either a Student's t-test, analyses of variance (ANOVA), or covariance analyses.
2. For longitudinal within-group analyses of cognitive and ADL progression, we will use either paired t-tests or repeated ANOVA models. Additionally, Kaplan Mayer survival curves and Cox proportional hazard models stratified by the individual group status (e.g. PD-MCI with and without cognitive-driven ADL impairment) will be applied to estimate the time period to PD-MCI or PDD conversion.
3. Associations between serum and CSF markers along with ADL and cognitive data will be carried out using multivariate regression analyses in order to evaluate the type of biomarker that best reflects the biological impact on phenotype and progression.

Reports on conversion rates of new-onset PD-MCI and PDD are highly variable between studies [5]. At a mean follow-up interval of around four years, the frequency of PDD in large

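### Aim 2.1 tracks ADL progression by a ratio of cognitive to motor impairment, so a patient whose cognitive ADL has worsened can be recorded as leaving the cognitive-driven group

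*Combined protocol and SAP*

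**What the plan says.** The second objective in Section 4.1 concerns how ADL impairment progresses. It has a single aim, "Aim 2.1: Evaluation of stability and/or progression of ADL status between baseline and follow-up", and the parenthesis that follows gives the status as FAQ_Q>1 versus FAQ_Q≤1. Aim 3.1 uses the term ADL status for the same split, there at baseline only.

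Section 3.2 defines the score. Of its construction it says "The quotient was formed by dividing the cognitive aspect" by the motor one, with 1 added to each. The cognitive subscore FAQ_C uses items 1, 2, 7, 8 and 9. The motor subscore FAQ_M uses items 3, 4, 5, 6, 7, 8 and 10. Items 7 and 8 "were associated with both motor and cognitive function and were therefore included into both scores as a constant". A value above 1 is read as more cognitive than motor impairment.

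Section 7 gives the method: "For longitudinal within-group analyses of cognitive and ADL progression, we will use either paired t-tests or repeated ANOVA models". It does not name the ADL score, and no section says how a move from >1 to ≤1 is to be read.

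**The concern.** A measure of progression should separate patients who got worse from patients who did not. FAQ_Q compares two kinds of impairment with each other, so it can stay level or fall while both kinds increase. The follow-up interval is about 46.6 months (Section 6.1), long enough for motor and cognitive items both to change.

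At stake is the reading of Aim 2.1. A patient whose cognitive ADL has worsened, but whose motor ADL has worsened by sufficiently more, would be tabulated as having changed from cognitive-driven to motor-driven. The cognitive-driven state could then look unstable in patients in whom it has deepened. Loss of independent living is what Section 3.1 uses to separate PDD from PD-MCI, so patients with substantial ADL loss are the ones the study most needs to describe correctly.

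**Working it through.** **Inputs, all from Section 3.2.** Ten items, each scored 0 to 3, higher being worse; the two item sets above; FAQ_Q = (FAQ_C+1)/(FAQ_M+1), where each subscore is a sum of item score divided by item maximum; cut-off >1.

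**Plan's own figure.** 10 items × 3 = 30, the stated maximum. FAQ_C runs from 0 to 5 and FAQ_M from 0 to 7.

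**The cut-off.** In points, let C = items 1+2+9 (0 to 9), M = items 3+4+5+6+10 (0 to 15) and K = items 7+8 (0 to 6). Multiplying numerator and denominator by 3 gives

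FAQ_Q = (C+K+3)/(M+K+3).

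K cancels at the cut-off, so FAQ_Q>1 exactly when D = C − M is above 0.

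**When status changes.** For a patient with baseline D above 0, status moves to ≤1 exactly when (rise in M) − (rise in C) is at least baseline D.

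| Constructed case | Baseline C, M, K | FAQ_Q | Follow-up C, M, K | FAQ_Q | Excess motor rise vs baseline D |
|---|---|---|---|---|---|
| Total 1 to 17 | 1, 0, 0 | 4/3 = 1.33 | 7, 8, 2 | 12/13 = 0.92 | 2 vs 1: moves to ≤1 |
| Every item one point worse | 1, 0, 0 | 4/3 = 1.33 | 4, 5, 2 | 9/10 = 0.90 | 2 vs 1: moves to ≤1 |
| Every item one point worse | 3, 0, 0 | 6/3 = 2.00 | 6, 5, 2 | 11/10 = 1.10 | 2 vs 3: stays >1 |
| Equal point worsening | 1, 0, 0 | 4/3 = 1.33 | 3, 2, 0 | 6/5 = 1.20 | 0 vs 1: stays >1 |
| Motor worsens slightly more | 2, 0, 0 | 5/3 = 1.67 | 4, 3, 0 | 7/6 = 1.17 | 1 vs 2: stays >1 |

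The first case has follow-up items 1 to 10 equal to 2, 3, 1, 2, 1, 2, 1, 1, 2, 2.

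**Ceiling.** C cannot exceed 9, so once M is 9 or more FAQ_Q cannot exceed 1. The highest FAQ total with FAQ_Q>1 is C + M + K = 9 + 8 + 6 = 23. Every total from 24 to 30 is classed as motor-driven.

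**The two ends of the scale.** No impairment gives 3/3 = 1.00. Full dependence (C = 9, M = 15, K = 6) gives 18/24 = 0.75. From a start of 1.33, both outcomes are recorded as the same move from >1 to ≤1.

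**FAQ_Q as a continuous score.** In a paired comparison, 1.33 to 1.00 (recovery) and 1.33 to 0.75 (full dependence) are both falls. Shared items distort it further: C = 9 with M = K = 0 gives 12/3 = 4.0, and adding K = 6 gives 18/9 = 2.0, a halving with nothing improved. That last comparison bears only on continuous use, since both values are above 1 and status does not change.

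**The case against.** The best counter-argument is that Aim 2.1 need not mean change in FAQ_Q status. Its parenthesis could name baseline groups, as in Aim 3.1, and paired t-tests and repeated ANOVA suit a score rather than a two-level status. Aim 3.3 mentions ADL decline without tying it to FAQ_Q, and Section 8.5 puts IQ-CODE forward as a marker of cognitive ADL progression. This shows that better measures are available. It does not settle the point, because none of them is linked to Aim 2.1, the aim refers to status at both time points, and continuous FAQ_Q has the same weakness.

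Four stronger readings are tempting and are not supported:

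- **That motor worsening equal to or greater than cognitive worsening always changes status.** Equal point worsening leaves D unchanged, and a larger motor rise matters only if the excess reaches baseline D.
- **That FAQ_Q always falls as disease advances.** Worsening confined to items 1, 2 and 9 raises it. A strongly motor-weighted patient can also rise while staying ≤1: five motor items at 1 give 3/8 = 0.375, and one point more on every item gives 8/15 = 0.533.
- **That fully dependent patients, or many PDD converters, will be misread.** Sections 6.2.1 and 6.2.2 require participants to communicate, comply and consent, so 0.75 at 30/30 is a scale limit rather than an expected observation. The documents give no item-level data from which to estimate a number.
- **That the main hypothesis fails.** It uses baseline FAQ_Q to predict later PDD, and Section 8.2 bases that diagnosis on Task Force criteria, not on change in FAQ_Q. The plan also nowhere calls a move to ≤1 an improvement.

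**Conclusion.** The point holds for Aim 2.1 and for the ADL-progression line of Section 7. FAQ_Q status cannot by itself show progression: it gives recovery and severe loss the same transition, and it cannot exceed 1 once the five motor items total 9 or more. These results are exact consequences of the Section 3.2 formula and need no assumption about patients. They do rest on reading Aim 2.1 as a comparison of FAQ_Q status at the two visits, which its wording supports.

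The number of patients affected is unknown. It depends on baseline D and on how much more the motor items worsen than the cognitive ones, and the documents report neither. Aim 3.1 is not affected. The change matters because Aim 2.1 is the only aim of a stated objective.

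**What to change.** In Aim 2.1 and Section 7, define ADL progression as the change in FAQ_C and the change in FAQ_M from baseline to follow-up, analysed separately with the paired or repeated-measures methods already planned. Because items 7 and 8 sit in both subscores, FAQ_C can rise for motor reasons. Add a sensitivity analysis on the non-shared items: 1, 2, 9 for cognitive and 3, 4, 5, 6, 10 for motor.

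Keep follow-up FAQ_Q status as a secondary description of balance, cross-tabulated with change in FAQ_C. State that a move from >1 to ≤1 will not be interpreted as loss or reversal of cognitive-driven impairment unless FAQ_C itself fell.

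The cost is a change of wording and two progression measures in place of one status. No new data are needed, since both subscores are already computed to form FAQ_Q.

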6.1. Study population

Between March 30th, 2014 and December 31th, 2017, we recruited a large cohort of 262 PD patients within the frame of the “Amyloid-Beta in cerebrospinal fluid as a risk factor for cognitive dysfunction in Parkinson’s Disease” (ABC-PD, ethic protocol 686/2013B01) study. Of the total baseline sample, 43% were diagnosed with PD-MCI (63% males, mean age of 67.2 ± 7.7 years) whereas 57% had normal cognitive function (61% males, mean age of 65.4 ± 8.7 years). Mean disease duration of the total sample was 5.1 ± 3.9 years.

We propose to follow-up the already existing ABC-PD cohort described above with a longitudinal assessment including neuropsychological in-depth endophenotyping and CSF biomarker analyses. The estimated mean follow-up interval is 46.6 ± 6.6 months.

6.2. In- and exclusion criteria for follow-up assessment

The investigator will ensure that all patients considered for the study meet the inclusion and exclusion criteria described in Sections 6.2.1 and 6.2.2.

6.2.1. Inclusion criteria

- 50–90 years of age.
- Diagnosis of PD according to the United Kingdom Brain-Bank criteria.

- Ability to communicate well with the investigator, to understand and comply with the requirements of the study.
- Provide written informed consent to participate in the study and understand their right to withdraw consent at any time without prejudice to future medical care.

6.2.2. Exclusion criteria

- Any disability that may prevent the subject from completing the informed consent form or other study requirements.
- Other neurodegenerative disease which renders the subject unable to communicate well with the investigator or to understand and comply with the requirements of the study.
- Participation in any clinical investigation of a new investigational compound or therapy within 4 weeks prior to baseline visit, and for any other limitation of participation based on local regulations.
- Alcohol, medication or drug dependency or abuse (except for nicotine).
- History of brain disease other than PD, e.g. head trauma, stroke, encephalitis, etc.

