REM Sleep behavior questionnaire (RBDS-Q)	2 min
Apathy Evaluation Scale (AES)	3 min
Questionnaire for Impulsive-Compulsive Disorders in Parkinson's Disease-Short (QUIP-Kurz)	3 min
Unified Parkinson's Disease Rating Scale (UPDRS) Parts I-II	6 min
International Consultation on Incontinence Questionnaire-Short Form (ICIQ-SF)	2 min
Patient Perception of Bladder Condition (PPBC)	1 min
Top-10 Priority List	5 min
Saarbrücker Persönlichkeitsfragebogen (SPF)/ Interpersonal Reactivity Index (IRI)	5 min
Total time of clinical assessment:	185 min
Optional Home-based movement assessment (Accelerometer)	7 days

For this scientific study, all investigations will be performed in an ambulatory setting and need the study participants to be available for at least 3 hours and 5 minutes, not including the optional blood marker sampling (blood: 15 min, CSF: 30 min). To evaluate the association between the onset and severity of both motor and non-motor symptoms which might indicate disease progression and are therefore more pronounced in PD patients with mild ADL dysfunction, a comprehensive clinical assessment will be conducted.

- If patients agree to the optional CSF and/or blood collection (see also 8.6):
 - Blood collection 15 min
 - CSF 30 min**Total time for biomarker sampling:** 45 min

Caregiver assessments:

To validate the patient's self-impression, the following caregiver questionnaires and interview scales will be applied, needing caregivers to be available for at least 40 minutes. Caregiver assessments will only be performed if the respective patient has agreed to the interview.

Table 2: Overview of caregiver assessments

Assessment	Time
Explanation of the study requirements	10 min
Interview-based ratings:	
Informant Questionnaire on Cognitive Decline in the Elderly (IQ-CODE)	6 min
Tübinger Activity of Daily Living Inventory for Parkinson's disease	6 min
Questionnaires:	
Pfeffer Functional Activities Questionnaire (FAQ)	4 min
Bayer Activities of Daily Living Scale (Bayer ADL)	5 min
Top-10 Priority List	5 min
Saarbrücker Persönlichkeitsfragebogen (SPF)/ Interpersonal Reactivity Index (IRI)	4 min
Total Time of caregiver assessment:	40 min

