8.5. Caregiver ADL assessments

Caregiver assessments have a crucial role determining a diagnosis of PDD, by examining whether patients are able to care for themselves and carry out their daily activities. The Bayer Activities of Daily Living (Bayer ADL) scale consists of 25 questions answered by the caregiver that evaluate the patient's ability to perform activities of daily living. The Informant Questionnaire on Cognitive Decline in the Elderly (IQ-CODE), a brief screening tool of dementia, compares patients' current abilities to how they were two years ago. This provides a useful marker for cognitive ADL progression, as well as helps to distinguish cognitive decline from normal aging. The caregiver assessment of ADL using the FAQ allows us to compare patient and caregivers' evaluation of ADL impairments.

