10.3. Information and informed consent

Prior to the respective assessments, every prospective participant will be informed in oral and written form about the general goal of the study and how the assessments will be performed. In particular, the informed consent form will contain comprehensive information about contents, objectives, duration, procedures, voluntariness, and possible risks of the study participation. Any kind of questions will be considered and answered. In case of agreement for study participation, the participant has to sign two copies of the informed consent form. One will be given to the participant, and the other form will be stored at the local study centre in a separate folder (not in the medical records).

In addition to the PD patients, a caregiver will be contacted and interviewed. Therefore, informed consent will also be obtained from the patient's caregiver using a separate caregiver

informed consent form. The patient will be asked to choose the caregiver who will then be contacted for the caregiver assessment.

11. Insurance

The study is covered by the clinical trials insurance. No travel accident insurance will be offered. However, for CSF sampling, patients will be additionally insured to increase their safety in case of the above mentioned adverse events (AEs) or serious adverse events (SAEs) after lumbar puncture. SAEs are unanticipated, serious, and possibly related to the study procedures. SAEs will be reported to the local ethical committee in accordance with requirements. An appropriate application for a selected insurance will be filed with the help of the insurance management (contact person: [name]) of the University of Tübingen. The insurance confirmation and the insurance conditions will be passed on to the Ethics Committee after the insurance has been taken out. The patient information is also provided with the most important information (contents and exclusions of the insurance, compensation amount, period of insurance, name and contact details of the insurer, insurance certificate number, obligations of the insured according to the insurance conditions) and the insurance confirmation and the insurance conditions are attached to the subject information as soon as they are available.

Number of insurance police: 57 010311 03013

Insurance Period: 15.08.2018 until 31.12.2020

Amount of damage compensation: 500,000.00€ per participant, Maximum limit of indemnity is 5,000,000.00€ (for all 209 participants).

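### Entry to the follow-up visit depends on abilities that PDD can remove, and section 7 does not say how patients not seen or deceased enter the conversion analyses

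*Combined protocol and SAP*

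**What the plan says.** Section 6.2 is headed as criteria for the follow-up assessment and states: "The investigator will ensure that all patients considered for the study meet the inclusion and exclusion criteria". Section 6.2.1 requires "Ability to communicate well with the investigator, to understand and comply with the requirements of the study", together with written informed consent. Section 6.2.2 excludes "Any disability that may prevent the subject from completing the informed consent form or other study requirements", without an exception for disability caused by PDD. Under section 10.3 "the participant has to sign two copies of the informed consent form"; the caregiver form described there covers the caregiver's own participation. The consent forms listed in section 12 are attachments and were not available for this review.

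PDD is diagnosed at this visit by Level-II criteria (section 8.2). Section 8.5 says "Caregiver assessments have a crucial role determining a diagnosis of PDD", but according to section 8 "Caregiver assessments will only be performed if the respective patient has agreed to the interview".

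On attrition, section 6.3 says "A drop-out rate of 20% is expected for follow-up retention", so 209 patients are to be examined. One group is lost by an earlier choice: "Patients who did not agree to participate in a longitudinal study or who have asked not to be contacted" after the cross-sectional study are not approached again. Reasons for drop-out are to be recorded for analysis (section 6.3), and routine clinical data also enter the analysis (section 8.1).

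Section 7 plans relative risks, likelihood ratios, Kaplan-Meier curves and Cox models for conversion. It does not mention non-attenders or deaths.

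**The concern.** A patient is counted as a PDD converter only if examined. Examination requires understanding, compliance and the patient's own signature, which dementia can take away. Caregiver information, which the protocol treats as central to the diagnosis, also depends on the patient's agreement. Non-attendance can therefore be a consequence of the outcome. Section 3.1 also links PDD to nursing-home placement and death, so some converters may have died before the visit.

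At stake are the conversion rates of Aim 3.1 and the central comparison, PDD conversion in PD-MCI patients with FAQ_Q>1 against those with FAQ_Q≤1. If the method for non-attenders is not fixed beforehand, it will be chosen with the data in hand.

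**Working it through.** **The plan's own figures.** 262 × (1 − 0.20) = 209.6, stated as 209 (section 6.3), so 262 − 209 = 53 patients are expected not to be seen. Section 7 expects 27 to 58 PDD cases: 209 × 0.13 = 27.2 and 209 × 0.28 = 58.5. These are cited frequencies applied to the attendees, with no separate allowance for outcome-linked loss.

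**Bounds without a model.** With x cases seen, the rate among all 262 lies between x/262 and (x + 53)/262. For 27 seen this is 10.3% to 30.5%; for 58 seen, 22.1% to 42.4%.

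**Effect on conversion rates (illustration).** Let p be the true risk and 1 − f the ratio of converter to non-converter retention. Then observed risk = p(1 − f)/(1 − pf). The values of f are assumptions, and the cited frequencies are treated as true risks.

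| True risk p | f = 0.2 | f = 0.4 |
|---|---|---|
| 26% (PD-MCI, section 3.1) | 21.9% | 17.4% |
| 39.1% (PD-MCI, section 3.1) | 33.9% | 27.8% |
| 13% (whole cohort, section 7) | 10.7%, 22 of 209 | 8.2%, 17 of 209 |
| 28% (whole cohort, section 7) | 23.7%, 50 of 209 | 18.9%, 40 of 209 |

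**Effect on the FAQ_Q contrast (illustration).** Inputs:
- PD-MCI at baseline: 43% × 262 = 112.7 (section 6.1).
- Split 32.6%/67.4% (section 3.2, assumed to hold for all 262): 36.7 with FAQ_Q>1 and 75.9 with FAQ_Q≤1.
- Assumed true risks 45% and 20%, so overall 0.326 × 0.45 + 0.674 × 0.20 = 28%.
- Total PD-MCI retention held at 80% (90.1 seen), with equal non-converter retention in both groups.

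With no outcome-linked loss, 13.2 of 29.4 and 12.1 of 60.7 convert. RR = 0.45/0.20 = 2.25. SE of log RR = √(1/13.2 − 1/29.4 + 1/12.1 − 1/60.7) = 0.33, giving a 95% interval of 2.25 × exp(±1.96 × 0.328) = 1.18 to 4.28. LR+ = (16.5/31.7)/(20.2/80.9) = 2.09.

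One unequal case in full: with f = 0.4 in FAQ_Q>1 and 0.2 in FAQ_Q≤1, the observed risks are 0.27/0.82 = 32.9% and 0.16/0.96 = 16.7%, so RR = 1.98.

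| f in FAQ_Q>1 / FAQ_Q≤1 | Observed risks | RR | LR+ | Converters seen | SE log RR |
|---|---|---|---|---|---|
| 0 / 0 | 45.0% / 20.0% | 2.25 | 2.09 | 25.4 | 0.33 |
| 0.2 / 0.2 | 39.6% / 16.7% | 2.37 | 2.09 | 21.5 | 0.37 |
| 0.4 / 0.4 | 32.9% / 13.0% | 2.52 | 2.09 | 17.2 | 0.43 |
| 0.4 / 0.2 | 32.9% / 16.7% | 1.98 | 1.80 | 19.3 | 0.39 |
| 0.2 / 0.4 | 39.6% / 13.0% | 3.03 | 2.37 | 19.5 | 0.40 |

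Equal loss shifts the RR little and leaves LR+ unchanged. Unequal loss moves both, in either direction.

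**The case against.** Cohorts of this kind always lose patients, and consent requirements are an ethical necessity. That stands, and it is why only the analysis should change. Several further points also have force.

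- A reader might infer that the protocol excludes patients with PDD. It does not. The criterion on impaired communication names other neurodegenerative disease, section 7 expects PDD cases among those seen, and questionnaires may be completed at home (section 8.3). Only loss of the more severe cases can be argued.
- A reader might infer that 27 to 58 cases is too optimistic. That depends on attrition in the cited studies, which cannot be seen here. If their frequencies come from attendees, similar loss may already be included.
- A reader might infer a known bias in the central comparison. Under equal loss the RR goes from 2.25 to 2.37–2.52, well inside the 1.18 to 4.28 interval, and no passage shows that loss differs by FAQ_Q group.
- Some non-attendance was settled at or near baseline, before conversion, and is not outcome-linked. The illustration does not separate it. Its upper end is severe: at f = 0.4 in both groups, 14.6 of the 22.5 unseen PD-MCI patients (65%) would be converters.
- The Kaplan-Meier and Cox models could use partial follow-up from routine data. This is not a full answer: a patient with baseline data only adds no follow-up time, and censoring caused by dementia is informative.
- Drop-out reasons and routine data are already to be collected. They are sources, however; no section says how they yield PDD status or enter a denominator.

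**Conclusion.** The point holds as a gap in the analysis plan that should be fixed, with medium confidence. A stated selection rule can act on the outcome, about 53 patients are expected to be missing against 27 to 58 expected PDD cases, and section 7 gives no method for non-attenders or deaths. Attendee-only conversion rates may be too low, and fewer observed converters reduce precision. The direction of any bias in the FAQ_Q relative risk cannot be stated in advance, and the likelihood ratios change only if loss differs by group. Every size beyond the 53 patients and the simple bounds rests on assumed retention and, for the FAQ_Q contrast, assumed risks.

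**What to change.** Leave eligibility, consent and Level-II PDD among attendees as the main outcome unchanged. Add to section 7:

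1. Attendance and drop-out reasons by baseline FAQ_Q group, with deaths shown separately and refusal of contact after baseline separated from later loss.
2. A sensitivity analysis of the PD-MCI FAQ_Q contrast with inverse-probability-of-attendance weights from baseline data, among patients not known to have died, stating that it corrects only loss explained by baseline.
3. A sensitivity analysis that counts as PDD those non-attenders whose registered reason, or routine record where existing consent allows, shows dementia or loss of capacity from cognitive decline. The denominator is all baseline patients in the FAQ_Q group not known to have died without dementia. Remaining non-attenders, refusers included, are counted first as non-converters and then at the attendees' rate in their FAQ_Q group; both results are reported.
4. A statement that attendee-only conversion rates may be underestimates.

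The denominator rule in item 3 is needed because adding converters to the numerator alone creates bias. In the illustration with loss unrelated to outcome (true rate 28%), finding all 6.3 missed converters and dropping the other non-attenders gives (25.4 + 6.3)/(90.1 + 6.3) = 33%, and the RR falls to 50.6%/23.8% = 2.12. Counting the others as non-converters gives 31.7/112.7 = 28%.

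The cost is a few sentences and no new visits. Use of records must first be checked against the baseline consent (ethics protocol 686/2013B01, not seen) and the data-protection consent in section 10.1; if they do not cover it, item 3 uses registered reasons only. The downside is that status from reasons or records is less precise than Level II, so items 2 and 3 stay sensitivity analyses. Any route for consent by a representative is a matter for the ethics committee and is not part of this change.
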